7.5 Serious Adverse Event Reporting

In the event of an SAE, and/or additionally, any non-serious event of malignancy in patients 30 years of age and younger, whether related to HUMIRA® or not, the physician

[figure not shown]

will notify the AbbVie Immunology Clinical Safety Management Team within 24 hours of the physician becoming aware of the event by entering the serious adverse event or non-serious event of malignancy in patients 30 years of age and younger data into the electronic data capture (EDC) system.

[figure not shown]
If the EDC system is unavailable, the completed Serious Adverse Event Form should be submitted via fax:

For SAE concerns, contact the Immunology Safety Team at:

For any emergent patient safety concerns, please contact the physician listed below:

7.6 Pregnancy Reporting

Pregnancy in a registry patient must be reported to AbbVie within 1 working day of the site becoming aware of the pregnancy. Pregnancies will be collected from the date of the first dose of HUMIRA® in registry through 150 days following the last dose of registry drug or the end of the patient's participation in registry (whichever is longer).

Physicians should refer to their local prescribing information when making treatment decisions for patients who become pregnant while being treated with HUMIRA® in the registry. Patients who become pregnant and interrupt their HUMIRA® therapy should remain in the registry and should continue to be monitored for new SAEs and AEs of Special Interest.

All female patients who become pregnant while enrolled in this registry will be followed from the time the pregnancy is reported until the outcome of the pregnancy is known. Information regarding a pregnancy occurrence in a registry patient and the outcome of the pregnancy will be collected.

Pregnancy in a registry patient is not considered an adverse event. However, the medical outcome of an elective or spontaneous abortion, stillbirth or congenital anomaly is considered a serious adverse event and must be reported to AbbVie within 24 hours of the site becoming aware of the event.

7.7 Data Collection Procedures for Patients Who Participate in the Direct to HCP Process

For patients participating in the direct to HCP Process, the registry physicians or the patient's current health care provider will document any hospitalizations, surgeries, deaths, and any Adverse Event of Special Interest as defined in Section 7.1.2 and AEs of Special Interest that lead to permanent discontinuation of HUMIRA® annually via a paper or electronic questionnaire. The registry physician or current health care provider will assess and record the date of onset (where known), event description, use of HUMIRA® and other psoriasis medications.

[figure not shown]
These events will be reported to AbbVie from the time of registry enrolment up to 10 years, irrespective of any treatment interruption, any changes in treatment, or discontinuation of HUMIRA®.

Effectiveness data will not be collected in the HCP Process.

8.0 Ethics and Quality

Prior to any registry-related data being collected, the informed consent statement will be reviewed and signed and dated by the patient and the person who administered the informed consent. A copy of the signed informed consent form will be given to the patient and the original will be placed in the patient's medical record. A patient informed consent template will be provided to the registry physician.

If a patient is willing to participate in the HCP process, a copy of the signed Patient Authorization for Use/Disclosure of Data form will be obtained prior to the participation.

8.1 Quality Assurance

Prior to the initiation of the registry, physician and site personnel will be trained on the registry. Training will include a detailed discussion of the protocol, performance of procedures, paper PRO completion, and eCRF completion. Sites will be given a paper PRO and eCRF completion workbook for reference.

[figure not shown]
Monitoring visits will be performed at a subset of the sites. At the visits a quality assurance check will be performed against entries on the paper and eCRF and a quality assurance check will be performed to ensure that the physician is complying with the protocol and local regulations. The monitoring plan will detail how sites will be selected for the on-site monitoring visits and what data will be source data verified during the visit. Throughout the registry, CRO and AbbVie will periodically follow-up with the sites to ensure that SAEs and AEs of Special Interest are being reported.

All registry data will be entered via the eCRF. Only PROs completed by the patients will be done via paper CRFs and these will be submitted to be entered into the database. All eCRF information will be imported directly into the electronic data capture system. Any necessary corrections will be made to the database and documented via addenda, queries, source data clarification forms or an audit trail. A manual review of selected line listings will also be performed at the end of the registry. All paper questionnaires (including direct to HCP questionnaire) will be entered into the database by the CRO data management group upon receipt.

9.0 Case Report Forms

All data associated with this registry will be collected and reported electronically (eCRF) via a web address and secure password. Patient self-administered questionnaires will be completed on paper forms and then submitted to be entered into the database.

At the Enrollment visit, the physician will complete the Enrollment eCRFs by obtaining and recording all available required information, as outlined in Section 6.5.

At subsequent visits corresponding to the schedule of assessment (Table 1), the physician will complete the appropriate eCRF by obtaining and recording all available information. Since this is an observational registry conforming to usual clinical practice, data from patient visits that most closely correspond to the recommended schedule of assessment at Months 3, 6, 12, 18, 24, and every 6 months through the end of registry participation will be collected.

Paper/electronic questionnaires will be generated for patients that have discontinued from the registry for any reason and signed the authorization for data release for the completion of the HCP questionnaire in the direct to HCP process.

Upon completion of or termination from the registry, all patients should have a Study Completion eCRF completed as well as an assessment of their current medical conditions.

10.0 Data Analysis Plan

10.1 Analyzable Populations

All Treated Patient Population is defined as patients who receive at least one dose of HUMIRA® in the registry.

New Prescription Patient Population is defined as patients who have newly initiated HUMIRA[®] therapy within 4 weeks prior to the entry into the registry and who receive at least one dose of HUMIRA[®] in the registry (the New Prescription Population is a subset of the All Treated Patient Population).

The All Treated Patient Population and the New Prescription Patient Population will be used for safety and effectiveness analysis.

In addition, the Intermittent Treatment Population, defined as patients who have at least 2 treatment interruption periods with at least 3 treatment periods (Figure 1), will be used for the safety analysis. A treatment interruption period is defined as greater than 70 consecutive days during which the patient does not receive any HUMIRA® treatment. The treatment interruption period starts from 71 days after the last dose of HUMIRA® in

the preceding treatment period and up to the day prior to the first dose of $HUMIRA^{@}$ in the subsequent period. A treatment period is defined as at least one dose of $HUMIRA^{@}$ up to 70 days after the last dose of $HUMIRA^{@}$.

Last Dose First Dose First Dose Day 70 Post-TI (#1) Pre-TI (#1) On Drug Off Drug = TI Drug On 70 days after last dose Treatment Period 1 -Treatment Interruption 1 -**Treatment Period** through 70 days after last dose Begins Day 71 after last dose 2, 3....N

[figure not shown]
Figure 1. Treatment Period and Treatment Interruption (TI) Period

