6.1.1 Inclusion Criteria

A patient will be eligible for participation in this registry if he/she meets all of the following criteria:

1. An adult patient (18 years of age or older) with chronic plaque psoriasis who has been prescribed HUMIRA® therapy according to the local product labeling and meets one of the following criteria:

Newly initiated (within 4 weeks of registry entry) on HUMIRA® therapy; Initiated HUMIRA® therapy in the past and:

Has received continuous (no more than 70 consecutive days off drug) HUMIRA® therapy and the physician can provide source documentation of SAEs, AEs of Special Interest, and dosing information since initiation of therapy.

OR

Is entering after participation in an AbbVie HUMIRA (adalimumab) sponsored study and has received continuous (no more than 70 consecutive days off drug) HUMIRA® therapy after the completion of AbbVie sponsored study and the physician can provide source documentation of SAEs, AEs of Special Interest, and dosing information since initiation of commercial HUMIRA® (defined as a prescribed/non study drug).

- 2. Patient is willing to consent to data being collected and provided to AbbVie.
- 3. Patient is capable of and willing to give written informed consent and to comply with the requirements of the registry.

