10.3 Safety Analyses

[figure not shown]
Five main safety analyses will be reported from this registry: four analyses will summarize data through the end-of-registry (as defined in Section 12.0) and one will exclude the HCP Process. The details of the analyses are in Section 10.3.1, Section 10.3.2, and Section 10.3.3. If a patient is not covered by any of the analysis populations, but experiences an AE, this AE will be reported in a separate listing.

Observational AEs: SAEs, AEs of Special Interest and AEs that lead to permanent discontinuation of HUMIRA[®] occurring from the first day in the registry (enrollment visit or date of informed consent, through the last contact (as defined in Section 10.3.1) irrespective of drug treatment duration.

Registry Treatment-emergent AEs: SAEs, AEs of Special Interest and AEs that lead to permanent discontinuation of HUMIRA® occurring from the first recorded dose of HUMIRA® in the registry through 70 days after the last dose excluding AEs occurring during treatment interruptions (as defined in Section 10.1).

All Treatment Emergent AEs: SAEs, AEs of Special Interest and AEs that lead to permanent discontinuation of HUMIRA® occurring from the first recorded dose of HUMIRA® (initial dose) through 70 days after the last dose excluding AEs occurring during treatment interruptions (as defined in Section 10.1.

AEs for intermittent treatment: SAEs, AEs of Special Interest and AEs that lead to permanent discontinuation of HUMIRA® in the Intermittent Treatment Population.

Observational AEs excluding HCP process: SAEs, AEs of Special Interest and AEs that lead to permanent discontinuation of HUMIRA® occurring from the first day in the registry through the last contact excluding the HCP process.

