10.3.2 Analysis of Treatment-Emergent AEs

Registry Treatment-emergent SAEs, AEs of Special Interest and AEs that lead to permanent discontinuation of HUMIRA® and All Treatment-emergent SAEs, AEs of Special Interest and AEs that lead to permanent discontinuation of HUMIRA® will be summarized.

Registry Treatment-emergent AEs includes AEs occurring from the first day in the registry to 70 days after the last dose of HUMIRA® excluding:

- 1. AEs occurring during TI which are more than 70 days after the last dose of HUMIRA[®] prior to the TI.
- 2. AEs occurring on or after the first day of the registry, but before the date of the first dose of HUMIRA[®].

All Treatment-emergent AEs include AEs occurring from the first recorded dose of HUMIRA® (i.e., the initial dose) up to 70 days after the last dose of HUMIRA® (excluding AEs during TI which are more than 70 days after the last dose of HUMIRA® prior to TI). For patients enrolled from a prior HUMIRA® study or who initiated commercial HUMIRA® therapy before entering the registry, the summaries will include the events reported during their participation in the previous study, any events reported by retrospective data collection, and any events reported during this registry.

The number and percentage of patients experiencing treatment-emergent SAEs, AEs of Special Interest and AEs that lead to permanent discontinuation of HUMIRA® will be tabulated by body system and MedDRA® preferred term. Rates (event per 100 patient-years of exposure to HUMIRA®, defined in Section 10.2) of SAEs, AEs of Special Interest and AEs that lead to permanent discontinuation of HUMIRA® and the 95% confidence interval will be provided.

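### Patients already on drug at entry drop out of the main safety rates if an event ends treatment before their next dose, because Section 10.1 requires a dose after entry

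*Protocol*

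**What the plan says.** **Entry.** Section 6.1.1 of the protocol admits adults "Newly initiated (within 4 weeks of registry entry) on HUMIRA® therapy". It also admits earlier starters whose therapy has been continuous, meaning no gap longer than 70 days, provided that dosing and event records since initiation (of commercial drug for roll-over patients) are available.

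**Populations.** Section 10.1 says: "All Treated Patient Population is defined as patients who receive at least one dose of HUMIRA® in the registry". New Prescription patients are those who started "within 4 weeks prior to the entry into the registry and who receive at least one dose of" HUMIRA in the registry, and they are a subset of All Treated. The Intermittent Treatment Population is "defined as patients who have at least 2 treatment interruption periods with at least 3 treatment periods". On use, 10.1 says: "The All Treated Patient Population and the New Prescription Patient Population will be used for safety and effectiveness analysis".

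**Windows.** Observational AEs (10.3, 10.3.1) run from the first registry day to last contact, whatever the length of treatment, and 10.3.1 performs that analysis in All Treated. All Treatment-Emergent AEs (10.3.2) run from the initial dose, including doses before entry, to 70 days after the last dose. Registry Treatment-Emergent AEs are those "occurring from the first recorded dose of HUMIRA® in the registry through 70 days after the last dose excluding AEs occurring during treatment interruptions". Section 10.3.2 starts that window at the first registry day and then excludes "AEs occurring on or after the first day of the registry, but before the date of the first dose of HUMIRA".

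**Everyone else.** If a patient in none of the populations has an AE, then under 10.3 "this AE will be reported in a separate listing".

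**The concern.** A dose after entry is a sensible condition for someone who enrols before being treated. It is not sensible for someone who enrols already exposed, because an adverse event can be the reason that the next dose is never given. The event then removes its own patient from the analysis.

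The Observational analysis shows the inconsistency most clearly. It counts person-time from the first registry day, but only for patients who go on to take a registry dose. The stretch from entry to that dose therefore sits in the denominator while being closed, by construction, to any event that prevents the dose. The All Treatment-Emergent analysis has the same selection, although neither its window nor its exposure (10.2) needs a registry dose.

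Long-term safety is the primary objective (Section 5.0). What is at stake is early SAEs and AEs that end treatment. This matters most among new starters, where the gap falls in the first weeks of therapy. As 10.1 is worded, every New Prescription patient started before entry, so there the registry-dose condition can only remove exposed patients.

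**Working it through.** **1. What does 'in the registry' mean?** Section 10.2 starts registry exposure at the first dose in the registry and total exposure at the first recorded (initial) dose. The two are distinct, so the phrase in 10.1 means a dose after entry.

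**2. One patient traced through the text.** The patient starts HUMIRA 10 days before entry, consents, has a serious reaction on day 3 after entry and takes no further dose.

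| Section | Result |
|---|---|
| 6.1.1 | Eligible: started within 4 weeks |
| 7.4 | Event collected: it follows the first commercial dose |
| 10.3.2, All Treatment-Emergent window | Inside: 10 + 3 = 13 days after the initial dose, within 70 days of the last dose |
| 10.3, Observational window | Inside: after the first registry day |
| 10.1, All Treated and New Prescription | Out: no dose after entry |
| 10.1, Intermittent | Out: fewer than three treatment periods |
| 10.3 | Separate listing only |

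The event lies inside both windows and in neither set of rates. Sections 6.5 and 6.6 encourage such a patient to stay under observation, so the later follow-up is also outside the rates.

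**3. Lymphoma sizing (10.6).** Inputs: r = 0.0477/100 PY = 0.000477 per PY, limit 2r, one-sided 95% bound, 80% power.

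- Normal formula with null variance: PY = (1.645·√(2r) + 0.842·√r)² / r² = 21,038. The protocol states 21,500, about 2% more.
- Expected PY: 5,000 × 10 × 0.6 = 30,000 and 6,000 × 10 × 0.6 = 36,000, as stated.
- Excluding an assumed 0.5% to 5% of patients leaves 28,500 to 29,850 PY (5,000 enrolled) or 34,200 to 35,820 PY (6,000 enrolled). Exact Poisson power stays at about 90% to 96%.

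**4. Size of the SAE loss.** The document gives neither the gap from entry to first registry dose nor an SAE rate. Assumptions: mean gap d = 7, 14 or 28 days in all 6,000 patients; SAE rate λ = 3 to 6 per 100 PY; share s = 25% to 100% of gap SAEs that end treatment before the next dose.

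- Gap person-time = 6,000 × d / 365.25
- SAEs sent to the listing = gap person-time × λ × s
- Share of all SAEs = s × gap person-time / 36,000 (λ cancels)

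| d (days) | Gap PY | Gap PY / 36,000 | SAEs listed, lowest to highest | Share of SAEs (s = 25% to 100%) |
|---|---|---|---|---|
| 7 | 115 | 0.3% | 0.9 to 6.9 | 0.08% to 0.32% |
| 14 | 230 | 0.6% | 1.7 to 13.8 | 0.16% to 0.64% |
| 28 | 460 | 1.3% | 3.4 to 27.6 | 0.32% to 1.28% |

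Expected lymphomas in the gap at 0.0477/100 PY are 0.05, 0.11 and 0.22.

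**The case against.** **The case is foreseen and disclosed.** Section 10.3 provides the listing, and the summary of changes in 1.1 shows that this was a deliberate clarification. Requiring a dose is a common safety-set convention. It stands that the events remain visible and that the convention suits patients not yet dosed at entry. But a listing enters no numerator or denominator, and the convention normally means any exposure, which these patients have had.

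**A reader might infer that every safety population demands a registry dose and that such a patient is expressly barred from every rate.** The text does not go that far. The Intermittent definition has no such condition, although someone who stops for good near entry would rarely meet its three-period rule. Only 10.3.1 names All Treated outright. Sections 10.3.2 and 10.3.4 name no population for their main analyses, so exclusion there follows from 10.1. Section 10.3.3 also promises reference summaries for patients outside the Intermittent population, which could be read to include these patients, though not expressly as rates.

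**A reader might infer a sizeable downward bias in all rates.** That is not supported. Patients can also miss a registry dose through withdrawal or loss to follow-up, and removing event-free person-time of that kind raises a rate. The downward direction holds for events that end treatment.

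**A reader might see a substantive conflict between the windows in 10.3 and 10.3.2.** Read literally, exclusion 2 removes nothing for a patient who was on drug before entry, so the two sections differ. If its first dose is taken to be the first registry dose, the windows agree with each other and with registry exposure in 10.2. That is a drafting gap and no evidence of bias.

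**Conclusion.** The point holds as a weakness in how the protocol fixes its populations. For patients exposed before entry, membership of All Treated and New Prescription depends on a later dose that an adverse event can prevent. This takes early treatment-ending events out of the Observational rates and, through 10.1, out of the All Treatment-Emergent rates. The protocol sets these definitions itself, so an analysis plan that follows 10.1 would carry them forward.

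The effect is probably small: about 1% or less of SAEs in most of the range shown, and 1.3% at its upper end. That range rests wholly on assumed gaps, rates and stopping shares. For AEs leading to permanent discontinuation, and for New Prescription alone, the document offers no basis for a figure. The lymphoma sizing is unaffected. The reasons to change are that the selection depends on outcome and that it is avoidable with data already collected.

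**What to change.** - **Section 10.1, with matching wording in 10.3, 10.3.1, 10.3.2, 10.3.4 and 10.3.5.** For the Observational analyses (with and without the HCP process) and the All Treatment-Emergent analysis, define the population as enrolled patients with at least one recorded HUMIRA dose before or after entry. For the New Prescription versions of these analyses, drop the registry-dose condition and keep the 4-week criterion.
- **Registry Treatment-Emergent analysis.** Keep the registry-dose condition, the window and the exposure start at the first registry dose, for this analysis only.
- **Section 10.3.2, exclusion 2.** After the reference to the first dose of HUMIRA, add 'in the registry', so that it matches 10.3 and 10.2.

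Registry exposure should not be moved back to enrolment for patients with a recent dose. Section 10.2 ends exposure 14 days after the last dose. A patient enrolled 40 days after a last dose who never resumes would have 14 − 40 = −26 days of exposure, while AEs still counted to day 70.

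The cost is wording and programming, with a slightly larger population. Section 6.1.1 already requires the dosing history, so no new data are needed.

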6.5 Registry Conduct

Physicians will be provided with a registry kit that includes a protocol, patient informed consent forms, access to electronic Case Report Forms (eCRFs), including SAE Report Forms, specially designed eCRFs to collect AEs of Special Interest and paper patient

questionnaires to collect Patient Reported Outcomes (PRO) (United States only). Physicians will determine the appropriate therapy for each patient in accordance with the locally approved label. The decision to prescribe HUMIRA® to the patients should be made separately from, and prior to the decision to enroll them into the registry.

The physician will follow the patient during regular office visits at intervals as determined by routine clinical practice or as recommended by national guidelines.

At the enrollment (baseline) visit, the physician will complete the Enrollment eCRFs by obtaining and recording all of the available required information. All SAEs and AEs of Special Interest (Table 2) that occurred since the first commercial dose of HUMIRA® will be collected on a specially designed questionnaire/source document for entry into EDC.

Information about medications taken for Psoriasis will be recorded on the eCRF at enrollment and during the regularly scheduled visits that are closest to Months 3, 6, 12, 18, 24, and every 6 months thereafter through Month 120. While the physician may deem it appropriate and necessary to have the patient return for additional visits during the observation period, data will be collected via electronic Case Report Forms (eCRFs) only at the intervals that most closely correspond to those described above. However, information related to safety should be captured at any time using the appropriate eCRFs.

Physicians should treat their patients as they would in their routine clinical practice. At any time, patients and physicians may choose to interrupt HUMIRA® therapy for any reason. Patients that intermittently stop treatment (Section 10.1) should continue to be monitored during their treatment interruption for safety (SAEs and AEs of Special Interest) and effectiveness, if applicable. These patients will be questioned for changes in their psoriasis medications and medical history at their regularly scheduled visits.

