6.5.5 Physician's Global Assessment and Patient Reported Outcome Measurements

When applicable, information about the effectiveness of HUMIRA® therapy will be provided by the physicians and the patients. The Physician's Global Assessment (Appendix C) will be collected to assess the effectiveness of therapy at all registry visits at all sites. Effectiveness of therapy provided by the patient will be collected at US sites only utilizing patient reported outcomes (PROs) beginning at the enrollment visit and subsequently as outlined in Table 1. Effectiveness measures will be collected for patients participating in the registry regardless of HUMIRA® treatment. However effectiveness measures will not be collected as part of the HCP process. The PROs to be utilized include: Dermatology Life Quality Index (DLQI) (Appendix D), Patient Health Questionnaire PHQ-9 For Depression (PHQ-9) (Appendix E), Healthcare Resource Utilization (Unscheduled Outpatient Visits, Emergency Room Visits and Hospitalizations Questionnaire) (Appendix F), Work Productivity and Activity Impairment Questionnaire: Specific Health Problem V2.0 (WPAI:SHP) (Appendix G), Rosenberg Self-Esteem Scale (Appendix H, Census Socio-Demographic Questionnaire (Appendix I), Medical Outcomes (MOS)-Social Activities Scale (Appendix J), Psoriasis Impact and Experience (Appendix K), Illness Cognition Questionnaire (Appendix L), Insurance Status (Appendix M), and Patient Global Assessment (Appendix N).

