7.4 Adverse Event Collection Period

SAEs, AEs of Special Interest, and AEs that lead to permanent registry HUMIRA[®] discontinuation will be reported to AbbVie starting from the first commercial dose of HUMIRA[®] or when the initial informed consent is signed, (whichever date is earlier), throughout the patient's participation in the registry, or direct to HCP process, until satisfactory resolution or for 70 days after their last dose of registry drug (whichever period is longer) to further evaluate safety.

Follow-up received on ongoing SAEs and/or AESIs post registry conclusion should be reported using standard Post-Marketing Reporting.

[figure not shown]
For patients participating in the direct to HCP process, surgeries, hospitalizations, deaths, events listed as AEs of Special Interest (Table 2), and AEs of Special Interest that lead to permanent discontinuation of HUMIRA® will be collected.

In the event HUMIRA[®] therapy is interrupted (Section 10.1), the patient will remain in the registry and continue to be monitored during the treatment interruption for SAEs and AEs of Special Interest and will be questioned for changes in their psoriasis medications and medical history of the event at their registry visits. If treatment with HUMIRA[®] is permanently discontinued for any reason, the reason will be recorded and the patient should be encouraged to remain in the registry for the full 10 years.

For patients enrolled from a prior AbbVie HUMIRA® study, ongoing events at the time of registry entry will be collected.

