10.4 Effectiveness Analyses

Effectiveness parameters measured in this registry for patients enrolled in the US include: Physician's Global Assessment (PGA), Dermatology Life Quality Index (DLQI), Patient Health Questionnaire PHQ-9 For Depression (PHQ-9), Healthcare Resource Utilization, Work Productivity and Activity Impairment (WPAI:SHP), Rosenberg Self-Esteem Scale, Census Socio-Demographic Questionnaire, Medical Outcomes (MOS)-Social Activities Scale, Psoriasis Impact and Experience, Illness Cognition Questionnaire, Insurance Status, and Patient Global Assessment.

[figure not shown]
Descriptive statistics will be provided for the following variables according to the collection schedule outlined in Table 1:

- 1. PGA:
 - a. Proportion of patients achieving "clear."
 - b. Proportion of patients achieving "clear or minimal."
- 2. DLQI:
 - a. Proportion of patients achieving DLQI = 0.
 - b. Proportion of patients achieving DLQI = 0 or 1.
 - c. Change from baseline in DLQI.
- 3. PHQ9:
 - a. Change from baseline in PHQ9 total score.
- 4. Health Resource Utilization

- a. Proportion of subjects who had at least one event (e.g., hospitalization, ER, physician visits).
- b. Average number of events occurred per subjective who had at least one event.
- 5. WPAI-SHP: Change from baseline in the four impairment percentages:
 - a. Percent work time missed.
 - b. Percent impairment while working.
 - c. Percent impaired activity.
 - d. Percent overall work impairment.
- 6. Rosenberg Self-Esteem Scale: change from baseline in total score.
- 7. Census Socio-Demographic Variables: proportion of subjects in each category.
- 8. Medical Outcomes (MOS)-Social Activities Scale: change from baseline.
- 9. Psoriasis Impact and Experience: proportion of subjects who strongly agree, agree, not sure but probably agree, not sure but probably disagree or strongly disagree with any of the statements.
- 10. Illness Cognition Questionnaire: change from baseline in helplessness sub-score, acceptance sub-score and total score.
- 11. Insurance Status: proportion of subjects uninsured, or insured in any of the plan types.
- 12. Patient Global Assessment:
 - a. Proportion of patients achieving "Complete disease control."
 - b. Proportion of patients achieving "Complete disease control or good disease control."

Effectiveness data will be analyzed as observed, as this is an observational registry. Number of patients with non-missing baseline and visit values, baseline mean, visit mean,

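### As worded, the New Prescription Population leaves out patients first dosed after registry entry, so its change-from-baseline results rest on an on-drug baseline

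*Protocol*

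**What the plan says.** Section 10.1 sets two conditions for the New Prescription Patient Population: the patient newly started "therapy within 4 weeks prior to the entry into the registry and who receive at least one dose of" HUMIRA in the registry. Both must hold. The All Treated Patient Population needs only one registry dose.

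The eligibility criterion for new starters in Section 6.1.1 gives a window without a direction: "Newly initiated (within 4 weeks of registry entry) on" therapy. Section 6.1 has sites offer enrolment once the decision to use the drug has been taken, and Section 6.5 requires that decision to come before the decision to enrol. Neither section requires a dose first. Section 7.4 starts event reporting at the first commercial dose "or when the initial informed consent is signed, (whichever date is earlier"). Section 10.3.2 item 2 removes from the registry treatment-emergent analysis "AEs occurring on or after the first day of the registry, but before the date of the first dose of" HUMIRA.

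Section 6.5 fixes the baseline: "At the enrollment (baseline) visit, the physician will complete the Enrollment eCRFs". Section 6.5.5 has US sites collect "patient reported outcomes (PROs) beginning at the enrollment visit and subsequently as outlined in Table 1". Under Section 6.5.3 the retrospective collection covers serious events, events of special interest and exposure, not PGA or questionnaire scores.

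Section 10.4 plans change-from-baseline summaries, for example "Change from baseline in DLQI", and applies the effectiveness summaries to both the All Treated and the New Prescription populations. Section 10.3.5 repeats the observational and all-treatment-emergent event analyses in the New Prescription population.

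**The concern.** A population named for new prescriptions is where a reader will look for the course of patients from the start of treatment. For change from baseline, the most informative patients are those assessed before the first dose, and a patient who enrols and is then dosed is exactly that. The wording of Section 10.1 excludes this patient and keeps those already on drug at enrolment.

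At stake is the meaning of the change-from-baseline figures in this subset. They would describe change from a point up to 4 weeks into treatment, under a label that suggests change from before treatment. The subset would also miss the prospectively observed early period of patients first dosed in the registry.

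**Working it through.** The plan states no figure on this point, so nothing has to be reproduced. The check sets the sections side by side.

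**Step 1: can a patient enrol before the first dose?**
- Sections 6.1 and 6.5 tie enrolment to the decision to prescribe, not to a dose.
- Section 6.1.1 gives 4 weeks around or before entry; the text does not say which. A patient not yet dosed could qualify only through this new-initiation route, because the other routes require therapy already under way.
- Section 7.4 provides for consent earlier than the first commercial dose.
- Section 10.3.2 item 2 provides for registry time before a dose. This fits a patient not yet started, but it also fits the next injection of a patient already on drug, so it is consistent and not decisive.

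Taken together, the protocol allows the case. It does not say how often it occurs.

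**Step 2: apply Section 10.1 to each timing of the first-ever dose, given at least one registry dose.**

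| First-ever dose | All Treated | New Prescription | Enrolment assessment |
|---|---|---|---|
| 1 to 28 days before entry | in | in | after up to 4 weeks of drug |
| On the day of entry | in | not settled by the wording | same day as first dose; order not stated |
| After entry | in | out | before first dose |

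The only row with a certain pre-treatment assessment is the row left out.

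**Step 3: which results use the baseline?**
- Change from baseline in Section 10.4: DLQI, PHQ-9, WPAI, Rosenberg, MOS Social Activities and Illness Cognition. All are patient-reported and collected at US sites only (Section 6.5.5). These are affected.
- Visit-level proportions: PGA clear, PGA clear or minimal, DLQI 0, DLQI 0 or 1, and the Patient Global Assessment categories. These do not use the baseline and are unaffected.
- Events: for included patients the all-treatment-emergent analysis counts from the initial dose, so their early events are kept. Patients first dosed after entry are missing only from the New Prescription repeats in Section 10.3.5.

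**Step 4: direction and size.** Let f be the share of the eventual improvement already reached at the enrolment visit. Then

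recorded change = (1 − f) × change from before treatment.

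With f above 0 the recorded change is too small. The protocol gives no value of f. Purely as an assumption, f between 0.30 and 0.60 at week 4 gives 1 − 0.30 = 0.70 and 1 − 0.60 = 0.40, that is, 40% to 70% of the change for a patient enrolled at the end of the window. Patients enrolled sooner after the first dose would lose less. This shows how the bias works and does not estimate it.

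**The case against.** The strongest reply is that nobody eligible may be dropped at all. In Section 6.1.1, newly initiated stands opposite initiated in the past and can be read as a completed act. On that reading the criterion and Section 10.1 agree. The consent clause in Section 7.4 shows that consent may come before a commercial dose, not that this happens among new starters, and Section 10.3.2 item 2 has a second reading. This part stands: one may not infer that such patients certainly exist, and their number could be zero. It does not remove the fault, because Sections 6.1 and 6.5 leave the route open and Section 10.1 closes the subset to anyone who takes it. If the other reading is right, every clear member of the subset still has an on-drug baseline.

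A reader might also infer more than the protocol supports:
- That no analysed population contains a treatment-free baseline. Patients first dosed after entry are in All Treated, with their pre-dose assessments. They are only not shown separately there.
- That safety events are lost. Their events enter the All Treated observational analysis and fall within both treatment-emergent definitions. The New Prescription repeats are additional analyses under the subgroup heading.
- That all effectiveness results are biased. The visit-level proportions are not. Effectiveness is the secondary objective, and its analysis is descriptive and as observed.

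Finally, an on-treatment baseline in All Treated follows from openly admitting patients already on therapy, and is not an error. Details of display may be left to the SAP. The population definition, however, is fixed in the protocol, and an SAP that follows it inherits the exclusion.

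**Conclusion.** The point holds in a limited form. Section 10.1 is narrower than the enrolment provisions in Sections 6.1, 6.1.1, 6.5 and 7.4 allow. Read literally, it leaves out of the New Prescription subset the only patients with a pre-treatment PGA and patient-reported assessment, and every clearly included patient has a baseline taken after the first dose.

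The consequence is confined to the six change-from-baseline measures, the description of baseline status in this subset, and the subset's event tables, which lack these patients. If patients improve in the first weeks, change from baseline in the subset is likely understated. That early improvement is an assumption; the protocol gives no data on it. Neither the number of patients affected nor the size of the bias can be derived from the document. The main safety analyses do not lose these patients or their events.

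**What to change.** In Section 10.1, define the New Prescription Patient Population as patients whose first-ever dose falls within 4 weeks before registry entry, on the day of entry, or after entry under the new-initiation criterion, with at least one registry dose. State the direction of the 4-week window in Section 6.1.1 so that the two sections agree.

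In Section 10.4, add a change-from-baseline summary limited to patients whose enrolment assessment is on or before the first-ever dose. Keep the remaining change-from-baseline results, but label them as having an on-treatment baseline. The visit-level proportions need no change.

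The cost is one flag and one further set of tables. The first-dose dates are already needed for total exposure in Section 10.2. The subset with a pre-treatment baseline will be smaller and its estimates less precise; if it turns out to be very small, reporting its size is itself informative.
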